11.1.3 Parallel Qualitative Study

- Before start of study this will involve up to 10 patients and their carers
- After Stage 1 to include patients and their carers participating in Stage 1
- After Stage 2 to include patients and their carers participating in Stage 2

11.2 Statistical methods

11.2.1 Stage 1- Criteria for Stop/Go decision prior to Stage 2

At the end of Stage 1 there will be an assessment made by the SMG as to whether the Stage 2 study should go ahead. This decision will be made on the following criteria:

- 1. Percentage of patients attending the Surgical Neuro-oncology Clinic that are screened for emotional recognition deficits pre-operatively?
- 2. Percentage of patients with a deficit that are approached for the study?
- 3. Percentage of patients recruited that can complete all the assessments?
- 4. Percentage patients recruited that are able to complete the FACES intervention adapted for remote delivery with the assistance of a psychologist.

As per the sample size calculations described above, less than 50% would be deemed unacceptable (see Sample Size calculation above).

11.2.2 Stage 2 -Feasibility Assessments

- 1. To explore if we are able to screen patients with suspected high grade glioma attending clinic for deficits in emotional recognition. A deficit in emotional recognition is defined as scoring 11 or less on the emotional recognition test from the OCS-Bridge battery. To proceed with a larger, efficacy study we would need to be able to screen a minimum of 75% of new patients.
- 2. Acceptability will be assessed by calculating the percentage of screened patients that provided informed consent. The intervention will be considered feasible if at least 50% of patients meeting the eligibility criteria provided informed consent. This will be explored in more detail with the parallel qualitative study.
- 3. To Assess the compliance of the intervention and control arms, the percentage of patients who have completed all sessions will be calculated. Compliance will be concluded if at least 80% of patients complete all sessions.
- 4. Assess the acceptibility of the following established, validated outcome measures:
 - a. Diagnostic Assessment of Non-verbal Accuracy-2, Adult Faces (DANVA2-AF);
 - b. Part 1, which includes emotion recognition, of Emotion Recognition and Social Inference: The Awareness of Social Inference Test (TASIT);

IRAS: 270758 SCARF-BT Protocol Version Number: 1.1 c. The Toronto Alexithymia Scale-20 (TAS-20).

For each of these measures we will measure completion rates pre- and post-intervention. Acceptability will be explored further with our parrallel qualitative study.

- 5. To Assess the effect size of the intervention we will be assess changes in assessment measures (below) between the active (FACES) intervention group and the control group. Differences in scores will be assessed for:
 - a. DANVA 2-AF
 - b. TASIT using the TASIT version B at retest.
 - c. TAS-20 alexithymia.
 - d. QLQ30 and BN20 quality of life measures will be assessed using published minimal clinically important differences²⁵.
- 6. The difference between the Intervention group and the control group in Outcome Measures will be calculated together with 95% confidence interval. This will provide an early indicator that the intervention may make some difference and would be worth exploring in a larger, multicentre study as well as determining future sample sizes.

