7.5.1 Stage 1: the cohort study

The specific objectives for this part of the study are:

- 1. To examine if patients are able to complete the intervention with the support of a psychologist (defined as completing all 9 sessions of training).
- 2. To study, document and understand the iterative changes of a new technique for delivering a rehabilitation intervention (FACES - computer based training programme) and provide a narrative account of these changes until a stable technique has been developed (as described for Stage 2a IDEAL interventions¹⁸).
- 3. To assess acceptability of intervention as part of the parallel qualitative study.

- 4. Feasibility of assessment completion by recording established validated outcome assessments patients are able to complete
- 5. Feasibility of quality of life completion by both patient and carer

7.5.2 Stage 2: placebo-controlled feasibility randomised controlled trial The specific feasibility objectives for this stage will be:

- 1. To explore if we are able to screen patients for deficits in emotional recognition using OCS-Bridge (https://ocs-bridge.com/about). This is a tablet-based neuropsychological screening tool that uses three sets of tests (a) the Oxford Cognitive Screen (OCS) that assess language, semantics, orientation, reading, movement, number knowledge, mental flexibility, spatial attention and memory. (b) the Cambridge Attention, Memory and Perception Screen, and (c) standardised tests of mood (PHQ-9 and GAD-7)
- 2. To assess acceptability of the intervention, based on patients meeting the eligibility criteria that give consent for the study. This will be explored further as part of the parallel qualitative study.
- 3. To assess the ability to complete the active FACES intervention and control intervention.
- 4. To assess the acceptability of a number of established, validated outcome assessments as part of the parallel qualitative study.
- 5. To assess the impact on patient reported quality of life.
- 6. To assess the impact on patient's families.
- 7. To compare the impact of the active FACES intervention with the control intervention on scores for selected assessments.

Parallel Qualitative Study

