8.1 Inclusion Criteria

Patients recruited to this study will require the following inclusion criteria:

- 1. Patients pre-screened as part of the CogENT and SIND studies, scoring 11 or less on the emotional recognition test within the OCS-Bridge screening tool done pre-operatively (consistent with having a deficit pre-operatively)
- 2. Signed Informed Consent to SCARF-BT study
- 3. Aged 18 years and older
- 4. Imaging evidence of a high-grade glioma as assessed by a neuro-oncology MDT;
- 5. MDT and treating clinician recommend either biopsy or debulking of the tumour;
- 6. Patients scoring 11 or less on the emotional recognition test within the OCS-Bridge screening tool done post-operatively (consistent with having a deficit post-operatively)
- 7. Patients with WHO Performance status 0-2;
- 8. Patients suitable for oncological intervention (involving radiotherapy/ chemotherapy/ combining radiotherapy and chemotherapy);
- 9. For Qualitative Study only: speaks fluent English as the use of interpreters can alter patients exact words.
- 10. For Qualitative Study only: willing to participate in interviews and/or focus groups.

11.

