9.2 Study Screening

Only after the patient has consented to participate can the study specific assessments be performed.

The following assessments are required at screening:

- Informed consent
- Post-operative OCS-Bridge screening
- Personal details (Age at registration, Gender assigned at birth)
- Handedness
- Years in Education
- Age at leaving full time Education
- Clinical data:
 - WHO performance status (Refer to Appendix 2)
 - Histology of tumour and site of tumour
- Medical History (Disease Presentation, use of steroid and anti-epileptics to control symptoms)

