9.10 Schedule of Assessments

Time Point	Study Screening		Baseline		INT-1	INT-2	INT-3	INT-4	INT-5	INT-6	INT-	INT-8	INT-9	Post -INT
Time Frame	<2 weeks post-op		<2 weeks post-op		Week 1	Week 1	Week 1	Week 2	Week 2	Week 2	Week 3	Week 3	Week 3	< 2 weeks before radiotherapy
Consent	Χ													
OCS-Bridge screening ¹	Х			Ra										
Medical History ²	Х	Re		and										
Clinical data ³	Х	Regist		lom										
DANVA2-AF ⁵			X	nisati										X
TASIT ⁶		ration	X	1 ti										X
TAS-20 ⁷		1 -	X	on ⁴										X
QoL questionnaire ⁸			Х											Х
Instruct patient9			X											X
INTERVENTION ¹⁰				1	Х	Х	Х	Х	Х	Х	Х	Х	Х	
Patient feedback ¹¹														X

- 1. Potential patients will be identified pre-operatively (as part of CogENT and SIND studies) for deficits using the OCS-Bridge screening tool., After consent, the OCS-Bridge screening tool will be used post-operatively during screening to ensure deficits remain
- 2. Medical history will include disease presentation, pre-existing neurological, psychiatric or hearing or visual problems that will prevent testing.
- 3. Clinical data will include performance status, histology of tumour, site of tumour.
- 4. Randomisation Stage 2 only
- 5. DANVA2-AF = Diagnostic Assessment of Non-verbal Accuracy-2, Adult Faces.
- 6. TASIT = The Assessment of Social Interference Test (Part 1)
- 7. TAS-20 = Toronto alexithymia scale.
- 8. Quality of life will be assessed using the EORTCQLQ-30 scale with the BN20 brain tumour module
- 9. Patients will be instructed to use the intervention a patient manual is available.
- 10. Intervention is either the Emotional Recognition Rehabilitation Intervention the Faces Intervention or General Cognition Control Intervention
- 11. A final patient feedback session will be offered to explain the patient's problems and strategies for dealing with this

10 Assessment of Safety

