11.1 Number of patients

Up to 10 patients and their carers will be involved in interviews and/or focus groups prior to stage 1.

11.1.1 Stage 1

No formal sample size calculations were performed for Stage 1. Stage 1 will end either; when we understand the intervention and assessments are acceptable to patients and the technique is no longer evolving or; 10 patients have been recruited and undergone their final assessment - whichever is soonest.

Although we expect to screen more patients (up to a maximum of 20), we expect to recruit up to 10 patients to go forwards to the intervention at this stage.

SCARF-BT Protocol IRAS: 270758 Version Number: 1.1

11.1.2 Stage 2

For this study, our baseline scenario is where an uptake of above 50% or higher would seem acceptable while an uptake of the proposed intervention below 50% would be deemed unacceptable. With standard choices for significance level of 0.05 and a power of 80%, we would need a sample size of at least 19 subjects per arm to demonstrate feasibility

Acceptability/feasibility will be concluded if at least 50% of patients complete the proposed intervention. Assuming a significance level of 5%, 19 subjects in each arm would provide 80% power to observe at least 50% difference between the active FACES intervention and the control intervention.

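### Stage 2 item 2 calls the intervention feasible on the consent rate alone, while section 11.1.2 draws the same conclusion from completion, and no rule says which governs

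*Protocol*

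**What the plan says.** Four places in the protocol bear on this.

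- **Section 11.2.2, item 2.** Acceptability is measured by consent: "Acceptability will be assessed by calculating the percentage of screened patients that provided informed consent". The decision rule follows: "The intervention will be considered feasible if at least 50% of patients meeting the eligibility criteria provided informed consent". The item then adds: "This will be explored in more detail with the parallel qualitative study". No threshold or veto is attached to that exploration.
- **Section 7.5.2, Stage 2 objective 2** (repeated in the synopsis) frames the aim the same way: "To assess acceptability of the intervention, based on patients meeting the eligibility criteria that give consent for the study".
- **Section 11.1.2, Stage 2 sample size**, uses the same vocabulary for a different measure: "Acceptability/feasibility will be concluded if at least 50% of patients complete the proposed intervention".
- **Section 7.6.2 item 3 and section 11.2.2 item 3** deal with completion of all sessions. The first makes a rate above 80% a condition for further studies; the second concludes compliance at 80% or more.

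On timing, section 9.2 says: "Only after the patient has consented to participate can the study specific assessments be performed". Note 1 to the schedule in section 9.10 confirms the order: "After consent, the OCS-Bridge screening tool will be used post-operatively during screening to ensure deficits remain". Registration, baseline assessment, 1:1 randomisation and the nine sessions all come later.

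**The concern.** The subject of the item 2 rule is the intervention, but its only input is a decision taken before the patient has been allocated to anything. A refusal may reflect dislike of randomisation or of research soon after brain surgery. An agreement does not show that nine one-hour sessions proved tolerable. Consent is a sound measure of whether a randomised trial can recruit. It is a weak basis for saying that FACES is feasible or acceptable to those who receive it.

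Section 11.1.2 makes this more than loose wording, because it reaches the same named conclusion from completion. The final report could then state that the intervention is feasible under one section and not feasible under another, with nothing in the protocol to settle the matter. The choice would be made after the data are seen.

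**Working it through.** **The rules side by side**

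| Section | Measure | Threshold | Conclusion attached |
|---|---|---|---|
| 11.2.2 item 2 | consent | at least 50% | intervention feasible |
| 11.1.2 | completion of the intervention | at least 50% | acceptability/feasibility |
| 11.2.2 item 3 | completion of all sessions | at least 80% | compliance |
| 7.6.2 item 3 | completion of all sessions | above 80% | may proceed to further studies |

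The first two rows share a conclusion but not a measure. Rows two to four share a measure, at two thresholds. No section gives an order of precedence.

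**Does item 2 respond to what happens in the arms?** Take an assumed 76 eligible patients, of whom 38 consent: 38/76 = 50.0%, so item 2 is met. It stays met whether 0, 19 or all 38 of those randomised finish every session (0%, 50% or 100%). This follows from how the rule is built and needs no simulation.

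**How far apart can the two feasibility rules fall?**

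Inputs from the protocol: 38 patients randomised, 19 per arm; thresholds as in the table. The 11.1.2 rule is read as applying to the FACES arm.

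Assumptions, since the protocol gives no expected rates: true consent 60%, so about 38/0.60 = 63 eligible patients are asked; true completion 30%; patients independent.

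- Item 2: 0.50 × 63 = 31.5, so at least 32 must consent. P(X ≥ 32 | n = 63, p = 0.60) = 0.946.
- Section 11.1.2: 0.50 × 19 = 9.5, so at least 10 must complete. P(X ≥ 10 | n = 19, p = 0.30) = 0.033.

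Range for the assumed rates:

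| True consent (n = 63) | P(item 2 met) |
|---|---|
| 50% | 0.50 |
| 60% | 0.95 |
| 70% | 1.00 |

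| True FACES completion (n = 19) | P(at least 10), 11.1.2 rule | P(at least 16), 80% rule |
|---|---|---|
| 20% | 0.002 | 3.4e-9 |
| 30% | 0.03 | 1.5e-6 |
| 40% | 0.19 | 0.0001 |
| 50% | 0.50 | 0.002 |
| 60% | 0.81 | 0.02 |
| 70% | 0.97 | 0.13 |
| 80% | 1.00 | 0.46 |
| 90% | 1.00 | 0.89 |

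The first table does not depend on the second.

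**The two completion thresholds.** 0.80 × 19 = 15.2, so 80% needs at least 16 of 19. Any result from 10 to 15 completers in the FACES arm (53% to 79%) meets 11.1.2 and falls short of 80% in that arm. At a true completion rate of 70%, the 11.1.2 rule is met with probability 0.97 and the 80% rule with probability 0.13.

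**The consent denominator.** These figures take eligible to mean eligible on what is known before consent. Read literally, the criteria in section 8.1 include "Signed Informed Consent to SCARF-BT study", which would make the rate 100% by definition. Item 2 also names screened patients in one sentence and eligible patients in the next. Neither reading changes the main point, because every version of the rate is still a consent rate.

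**The case against.** The strongest reply is that completion is not ignored. Section 11.1.2 draws feasibility from it, section 7.6.2 item 3 blocks further studies unless it exceeds 80%, and no go decision is tied to consent alone. This stands. A reader might infer from item 2 that Stage 2 must find FACES feasible however badly it is received. The protocol does not support that reading: the insensitivity belongs to item 2 only, and poor completion would fail both the progression condition and, usually, the 11.1.2 rule.

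A second tempting reading is that feasibility is declared before anyone has used FACES. That is true of each Stage 2 patient at consent, but not of the trial. All Stage 1 patients receive FACES, and the stop/go review in section 11.2.1 considers their completion, with less than 50% deemed unacceptable.

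Third, consent is not devoid of information. Patients decide after reading an information sheet and having time to think, so agreement says something about prospective acceptability. This is fair, but the signal is mixed with willingness to be randomised and cannot speak to experience of the sessions.

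Fourth, high consent with low completion is no contradiction in itself; separate criteria exist to show just that. This would answer the point if the criteria had separate conclusions. Item 2 and section 11.1.2 do not.

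The parallel interviews help interpretation, but they are optional and have no stated power to alter the item 2 result.

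**Conclusion.** The point holds in a limited form. Item 2 and objective 2 attach a conclusion about the intervention to a measure of trial entry, and section 11.1.2 attaches the same conclusion to completion, with no stated hierarchy. Under the assumed 60% consent among 63 eligible patients and 30% completion, the two rules are met with probabilities of about 0.95 and 0.03. The size of that gap depends on the assumed rates. That item 2 ignores completion does not.

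The damage is to what the trial may say about feasibility. The decision to proceed to a larger study remains guarded by the 80% completion requirement. The point should be corrected before Stage 2 results are known, but it does not threaten the conduct of the trial.

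**What to change.** - In sections 7.5.2, 7.6.2 and 11.2.2 (item 2 in each) and the matching synopsis entries, limit the consent criterion to a conclusion about the trial: recruitment to a randomised trial is feasible if at least 50% of eligible patients consent. Use one denominator throughout, defined by what is known before consent.
- Draw the conclusion that the intervention is feasible or acceptable from session completion in the FACES arm, read with the interview findings.
- In section 11.1.2, reconcile the 50% completion rule with the 80% rule so that a single completion threshold governs that conclusion. Without this step the first two changes leave the 50% and 80% rules in open conflict.

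The cost is a wording amendment, with no new data, visits or patients. The downside is that a good consent rate alone would no longer earn the statement that the intervention is feasible.

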7.6 Study Outcome Measures

7.6.1 Stage 1: the cohort study

The specific outcome measures for this part of the study are:

- 1. Percentage of patients completing the intervention (defined as completing all 9 sessions).
- 2. Prospective recording of any changes to the administration, conduct and content of the rehabilitation intervention on a patient-by-patient basis.
- 3. The acceptability of the intervention will be explored through a parallel qualitative study (see below 7.6.3).
- 4. Percentage of patients completing the following validated outcome assessments
 - a. Diagnostic Assessment of Non-verbal Accuracy-2, Adult Faces (DANVA2-AF);
 - b. Emotion Recognition and Social Inference: The Awareness of Social Inference Test (TASIT), (part 1, EET subtest);
 - c. The Toronto Alexithymia Scale-20 (TAS-20).
- Percentage of patients and carers able to complete quality of life questionnaires.

7.6.2 Stage 2: placebo-controlled feasibility randomised controlled trial The outcome measures for this stage will be:

- 1. We will record the number of patients who undergo screening (the numerator) and the number of potentially eligible patients that attend clinic (the denominator). To proceed with a larger, efficacy study we would need to be able to use OCS-Bridge to screen a minimum of 75% of new patients.
- The percentage of screened patients meeting the eligibility criteria provide informed consent for the study. It will also be explored in more detail with the qualitative study (see below).
- 3. Percentage of patients who have completed all sessions for the FACES intervention (active intervention) and General Cognition Intervention (control intervention). To proceed to further studies this will again need to exceed 80%.
- 4. We will measure completion rates for the following established, validated outcome assessments pre- and post-intervention.
 - a. Diagnostic Assessment of Non-verbal Accuracy-2, Adult Faces (DANVA2-AF);
 - b. Part 1, which includes emotion recognition, of Emotion Recognition and Social Inference: The Awareness of Social Inference Test (TASIT);
 - c. The Toronto Alexithymia Scale-20 (TAS-20).

Acceptability will be explored with our parallel qualitative study.

- 5. Patient reported quality of life using the EORTC QLQ-30 with the BN20 brain tumour module¹⁹.
- 6. The impact of these problems on patient's families by asking interested family members to complete the Caregiver Quality of Life Index-Cancer (CQOLC).

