9.1 Patient identification

Patients that will be approached for this study will have already been recruited for one of the two studies detailed below. They will have had a cognitive screen using the OCS-Bridge screening battery as part of either:

- 1. The Cognition Evaluation for patients with Neurological Tumours (the CogENT study) - REC reference: 18/LO/0491.
- 2. Assessing impact of surgically-induced deficits on patient functioning and quality of life (SIND study) - REC reference: 19/WM/0152.

Patients will be identified pre and post operatively from our Multi-Disciplinary Team (MDT) process.

It is important to identify patients with pre-existing defects of emotional recognition preoperatively as a further 20% of patients acquire temporary deficits post-operatively. Whereas our data from the CogENT study suggests patients with deficits pre-operatively do not improve at delayed assessment. This method of identifying potential patients will therefore help exclude patients that may get better without any rehabilitation. Patients scoring 11 or less on the emotional recognition test that are part of the OCS-Bridge battery are considered to have a deficit.

Patients will be approached either in a clinic or remotely by telephone (in accordance with Trust guidance concerning COVID-19). The study will be introduced to the patient and they will be provided with the patient information sheet. Patients will be given time to think about participating and will be followed up by phone call/further phone call. Patients who wish to take part will then be invited to give written consent at their next clinic visit. The patient's carers will also be approached about completing their own assessments. Carers who wish to take part will give written informed consent.

SCARF-BT Protocol IRAS: 270758 Version Number: 1.1

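### The Stage 2 consent criterion has a circular and internally inconsistent denominator, so the 50% rule cannot be computed as written

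*Protocol*

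**What the plan says.** Two consecutive sentences of Protocol 11.2.2 item 2 describe the consent criterion. The first defines the measure: "Acceptability will be assessed by calculating the percentage of screened patients that provided informed consent". The second sets the threshold: "The intervention will be considered feasible if at least 50% of patients meeting the eligibility criteria provided informed consent". The matching outcome measure, 7.6.2 item 2, merges the two populations: "The percentage of screened patients meeting the eligibility criteria provide informed consent for the study".

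The eligibility criteria in 8.1 include, as item 2, "Signed Informed Consent to SCARF-BT study" and, as item 6, "Patients scoring 11 or less on the emotional recognition test within the OCS-Bridge screening tool done post-operatively".

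On timing, 9.2 states "Only after the patient has consented to participate can the study specific assessments be performed" and lists consent and the post-operative OCS-Bridge test among the screening procedures. Footnote 1 of the schedule in 9.10 also places that test after consent. The pre-operative score needed for inclusion 1 has another source, described in 9.1: "Patients that will be approached for this study will have already been recruited for one of the two studies detailed below". It is therefore known before SCARF-BT consent is sought.

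**The concern.** A consent rate is informative only if people who refuse can be counted in its denominator. Here the threshold is set on a population partly defined by having consented, and by a test that SCARF-BT performs only on those who have. The neighbouring sentence uses another population. The word screened is itself open to two meanings: the pre-operative OCS-Bridge done in the parent studies, or the Study Screening visit of 9.2, which requires consent.

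Consent among eligible patients is the stated quantitative basis for Stage 2 objective 2, acceptability. It is one of three numeric Stage 2 criteria, with 75% screened and 80% completing all sessions. Depending on the reading, one data set could be reported as a certain pass, as a figure driven mainly by how common the deficit is, or as true uptake. If eligible decliners are not logged as the trial runs, a later analysis plan cannot recover them.

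**Working it through.** **Inputs**

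- Threshold: 50% (11.2.2 item 2). It is a fixed cut-off, with no derivation to reproduce.
- Pre-operative deficit prevalence in the pilot: 9/16 (5.1.2).
- True uptake *c* among approached patients with a pre-operative deficit: not given in the protocol, so varied here as an assumption.
- Simplification: all patients with a pre-operative deficit are approached and are otherwise eligible.

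**Step 1. Who can be in each denominator**

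- (a) Meeting the eligibility criteria, read literally. Inclusion 2 requires signed consent, so the denominator is a subset of consenters. Rate = 100% for any *c*.
- (b) Screened, meaning the Study Screening visit of 9.2. Consent comes before the test, so the rate is again 100% for any *c*.
- (c) Screened, meaning all patients given the pre-operative test. Rate = prevalence × *c* = 0.5625 × *c*.
- (d) Approached, with a pre-operative deficit, and eligible on facts known before consent. Rate = *c*.

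**Step 2. The rate under each reading**

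| True uptake *c* | (a) and (b) | (c) 0.5625 × *c* | (d) |
|---|---|---|---|
| 20% | 100% | 11.3% | 20% |
| 40% | 100% | 22.5% | 40% |
| 60% | 100% | 33.8% | 60% |
| 100% | 100% | 56.3% | 100% |

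At *c* = 60%, readings (a) and (b) pass, (c) fails and (d) passes. At *c* = 40%, (a) and (b) still pass while (c) and (d) fail.

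**Step 3. What reading (c) demands**

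The rule passes when 0.5625 × *c* ≥ 0.50, that is *c* ≥ 0.50/0.5625 = 0.889.

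The prevalence is imprecise. The exact (Clopper-Pearson) 95% interval for 9/16 is 0.299 to 0.802. At the upper limit the required uptake is 0.50/0.802 = 62%. At the lower limit it is 0.50/0.299 = 1.67, which is unattainable. Reading (c) is therefore governed by a prevalence that has nothing to do with willingness to take part.

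**Step 4. Can the intended reading be computed?**

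Suppose the phrase means eligible apart from consent. Inclusion 6 still has to be settled for decliners. SCARF-BT does its post-operative test only after consent, and the protocol does not say that CogENT or SIND will supply a post-operative score for those who decline. The denominator is then undetermined for exactly the patients who matter.

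**Step 5. Behaviour under reading (d)**

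Take 76 approached patients as an illustration (38/0.50, the number giving 38 consents at 50% uptake; the protocol states no such figure). The binomial probability of at least 38 consents is about 0.0002 at *c* = 30%, 0.049 at *c* = 40% and 0.55 at *c* = 50%. Under (a) it is 1 at every *c*. So (d) gives a rule that separates low uptake from high uptake.

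**The case against.** The strongest reply is that no sensible reader would apply the literal wording. Signed consent in an inclusion list is a formality. Objective 2 speaks of eligible patients who give consent, and registration (9.3) records the date of consent and the confirmation of eligibility as separate items. On that view the rule means eligible apart from consent, and it can fail. Much of what defines eligibility (pre-operative score, age, imaging, MDT recommendation) is knowable without SCARF-BT consent. The parent studies might also hold post-operative scores, which the protocol does not rule out. Finally, the threshold is descriptive, carries no hypothesis test, and is supported by qualitative work.

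Much of this stands. A reader might infer that the criterion can never fail. The documents support that only for the literal threshold sentence and for the post-consent meaning of screened. Under the pre-operative meaning, or the likely intent, it can fail. What the reply does not remove is the conflict between two adjacent sentences, or the absence of any stated means of establishing inclusion 6 for decliners.

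A reader might also extend the point to the 75% screening criterion. The text does not support that. For that rate 7.6.2 states both parts: "We will record the number of patients who undergo screening (the numerator) and the number of potentially eligible patients that attend clinic (the denominator". The corresponding Stage 1 criterion in 11.2.1 refers to pre-operative screening of clinic attenders. Dependence on enrolment into the parent studies limits how the screening rate is interpreted, but it is not a circular definition.

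**Conclusion.** The point holds for the consent criterion only. As worded, its denominator is circular, and it conflicts with the sentence before it. The readings run from a certain pass at 100%, through a rate capped near 56% that needs about 89% uptake to pass, to true uptake. The charitable reading cannot be computed from what the protocol says will be known about decliners.

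The logic of the 100% result depends on no outside figure. The 56% cap and the 89% requirement rest on 16 pilot patients, and over the exact 95% interval the requirement runs from 62% to unattainable, so they show the scale of the problem and are not predictions. The claim that the rule cannot fail under any reading is not supported, and neither is any finding against the 75% screening rule.

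This is more than detail left to an analysis plan, because the protocol itself fixes the threshold and names the conflicting populations.

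**What to change.** In 7.6.2 item 2 and 11.2.2 item 2, use one definition:

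- **Numerator:** patients who sign SCARF-BT consent.
- **Denominator:** patients approached who have a pre-operative OCS-Bridge emotion score of 11 or less and meet the other criteria that can be assessed before consent. Inclusion 2 and inclusion 6 are left out, and the criteria that count are listed.

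Apply the 50% threshold to that rate. Log every approached patient, including decliners, prospectively. Report two further figures separately, so that neither is mixed into acceptability: the proportion of patients with a pre-operative deficit who were approached, and the post-operative screen-failure rate among consenters. Patients never approached should stay out of the consent denominator, since they could neither accept nor refuse. The denominator of the 75% screening rule stays as stated.

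The cost is a wording change in two sections and a screening log. The sponsor also accepts a criterion that can now fail.
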